Chemistry (including calcium and phosphorus) and hematology will be assessed at all study visits; a 12-lead electrocardiogram (ECG) will be performed at all study visits; and coagulation and urinalysis will be performed at baseline and end of study. At all study site

visits, blood samples will be collected for the assessment of thyroid hormone parameters including thyroid stimulating hormone (TSH), total triiodothyronine (T3) and thyroxine (T4), and free T3 (FT3) and free T4 (FT4). Lipids (as described in the secondary objectives) will be assessed at all study visits except for low density lipoprotein (LDL) particle analyses, which will be assessed at baseline, Week 12, and Week 16; LDL-C will be determined by ultracentrifugation at baseline and Week 12. Other biomarker assessments will include [REDACTED] and [REDACTED], assessed at all study visits. Follicle-stimulating hormone (FSH), total and free testosterone, luteinizing hormone (LH), creatine kinase MB isoenzyme (CKMB), troponin I, reverse T3, fibrinogen, alkaline phosphatase (ALP) isoenzymes, procollagen type 1 N-terminal propeptide (P1NP), and C-terminal telopeptide (CTX) will be assessed at baseline, Week 12, and Week 16; free testosterone will be calculated from total testosterone, [REDACTED], and serum albumin. Patients will be evaluated for adverse events throughout the study.

Following the first dose of MGL-3196 and thereafter, the dose of MGL-3196 will be down-titrated if TSH is below the lower limit of normal (LLN) with a >50% change from baseline confirmed on 2 consecutive assessments. Down-titrations will be as follows: the 100 mg dose would be decreased to 80 mg, and an 80 mg dose would be decreased to 60 mg. Following down-titration, TSH testing will resume according to the schedule of procedures. A second down-titration is permitted (i.e. to 40 mg).

A Data Safety Monitoring Board (DSMB) will oversee the study to ensure patient safety and to advise if any dosing alterations are recommended. The DSMB will review safety including thyroid hormone effects, liver-related events (ie, clinically meaningful elevations in liver enzymes alanine aminotransferase [ALT], aspartate aminotransferase [AST], and bilirubin), and other efficacy (lipid parameters) and safety data as needed. The DSMB will perform regularly scheduled reviews as well as an additional review if necessary.

DOSAGE FORMS AND ROUTE OF ADMINISTRATION:

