MGL-3196-06 employs a simple adaptive design, that will optimize dose for individuals randomized to MGL-3196. Based on studies in 129 individuals safely dosed for up to two weeks with MGL-3196, at doses ranging from 50- 200 mg per day, MGL-3196 drug exposure shows variability in exposure between individuals and higher exposure in some individuals, particularly at the 200 mg dose, which will not be used in the Phase 2 HeFH study. This is similar to statins, which are also liver-directed drugs that interact with liver and gut uptake transporters. MGL-3196 exposures are less variable at the lower doses, including 60-100 mg, that will be studied in this Phase 2 study. There are no studies that suggest that exposure to MGL-3196 will be different in patients with HeFH or that HeFH patients have consistent alterations in drug metabolizing enzymes or transporters which may be involved in MGL-3196 uptake by the gut or liver. Unlike statins, there has been no myopathy associated with higher drug exposures of MGL-3196 in humans or animal studies; nonetheless, the design of the HeFH Phase 2 trial is adaptive in that

dose adjustments of MGL-3196 will be made after 2 weeks of dosing to optimize exposure for the individual patient.

MGL-3106 exposure variability, which may relate to polymorphisms in drug metabolizing enzymes and transporters, may occur in some (~25-30%) patients in the HeFH study who may have higher than the target exposure (4000-9000 ng^{*} hr/ml) to MGL-3196 at the 100 mg dose. A few patients (10%) (likely to be non-LDL responders) may have drug levels lower than the target exposure. Therefore, the trial design is adaptive to optimize both safety and efficacy. Randomization will be 2:1, 100 mg MGL-3196 to placebo. The drug level of MGL-3196 reaches steady state in a few days. At the Week 2 clinic visit, an assessment of MGL-3196 PK will be performed, including measurement of the pre-dose and T_{max} (4 h) levels of MGL-3196. These two assessments will allow an accurate assessment of MGL-3196's total exposure. Between weeks 2-4, pending results of the PK measurements, all patients randomized to drug will be treated with 60 mg of MGL-3196. Based on the C_{max} value of MGL-3196 at Week 2, an unblinded clinical pharmacologist will assign MGL-3196 dose to the time period, Weeks 4-12. At Week 4, patients who had a Week 2 $C_{max} \geq 1500$ ng/ml will continue on 60 mg of MGL-3196 and those with $C_{max} < 1500$ ng/ml will be placed back on 100 mg/day.

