Chemistry (including calcium and phosphorus) and hematology will be assessed at all study visits; a 12-lead electrocardiogram (ECG) will be performed at all study visits; and coagulation and urinalysis will be performed at baseline and end of study. At all study site visits, blood samples will be collected for the assessment of thyroid hormone parameters including thyroid stimulating hormone (TSH), total triiodothyronine T3 and thyroxine T4, and free T3 (FT3) and free T4 (FT4). Lipids (as described in the secondary objectives) will be assessed at all study visits except for low-density lipoprotein (LDL) particle analyses, which will be assessed at baseline, Week 12, and Week 16; LDL-C will be determined by ultracentrifugation at baseline and Week 12. Other biomarker assessments will include [REDACTED] and high-sensitivity C-reactive protein (hsCRP), assessed at all study visits. Follicle-stimulating hormone (FSH), total and free testosterone, luteinizing hormone (LH), creatine kinase MB isoenzyme (CKMB), troponin I, reverse T3, fibrinogen, alkaline phosphatase (ALP) isoenzymes, procollagen type 1 N-terminal propeptide (P1NP), and C-terminal telopeptide (CTX) will be assessed at baseline, Week 12, and Week 16; free testosterone will be calculated from total

testosterone, [REDACTED], and serum albumin. Patients will be evaluated for adverse events throughout the study.

Following the first dose of MGL-3196 and thereafter, the dose of MGL-3196 will be down-titrated if TSH is below the lower limit of normal (LLN) with a >50% change from baseline confirmed on 2 consecutive assessments. Down-titrations will be as follows: the 100 mg dose would be decreased to 80 mg, and an 80 mg dose would be decreased to 60 mg. Following down-titration, TSH testing will resume according to the schedule of procedures. A second down-titration is permitted (i.e. to 40 mg).

A Data Safety Monitoring Board (DSMB) will oversee the study to ensure patient safety and to advise if any dosing alterations are recommended. The DSMB will review safety including thyroid hormone effects, liver-related events (ie, clinically meaningful elevations in liver enzymes alanine aminotransferase [ALT], aspartate aminotransferase [AST], and bilirubin), and other efficacy (lipid parameters) and safety data as needed. The DSMB will perform regularly scheduled reviews as well as an additional review if necessary.

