5 STUDY TREATMENTS

5.1 Treatment Groups

Patients who qualify for study inclusion will initially be randomized (2:1) to receive once-daily MGL-3196 100 mg or once-daily matching placebo given orally in the morning. All patients randomized to MGL-3196 will initially receive 100 mg QD through the week 2 visit, then 60 mg QD until the week 4 visit. At the week 4 visit, patients receiving MGL-3196 will be placed back on 100 mg if their week 2 MGL-3196 level 4 h postdose is < 1,500 ng/mL and described as the “100 mg group”; if the level of MGL-3196 \geq 1500 ng/ml they will continue to receive 60 mg QD for weeks 4-12 and will be described as the “60 mg group”. In summary, the assigned treatment groups are as follows:

- Placebo
- “100 mg group”: patients administered MGL-3196 100 mg for weeks 1-2, 60mg between week 2-4 visits, and 100 mg for weeks 4-12
- “60 mg group”: patients administered MGL-3196 100 mg for weeks 1-2 and 60 mg for weeks 2-12

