10.2.4 Sample Size Determination

Up to 105 patients in total will be randomized to 1 of 2 treatments (70 patient to MGL-3196, 35 patients to placebo). It is estimated that the treatment difference of percent change in LDL-C from baseline to Week 12 between any dose of the MGL-3196 group and the placebo group is about -20%. With a common standard deviation for the change in LDL-C at 20%, 27 patients per group to complete the Week 12 visit will provide 90% power with a two-sample t-test. The significance level is set as 0.025 for the consideration of multiplicity in comparisons of 2 daily dosing regimens of MGL-3196 vs. placebo group. The enrollment size is designed to allow for dropouts before the 12-week visit, and as such, patients who drop out of the study will not be replaced.

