APPENDIX A: SCHEDULE OF PROCEDURES (CONTINUED)

Visit	Screening	Baseline	Week 2	Week 4	Week 8	Week 12/ Early Term	Week 16 (Follow-Up)
Study Day [Window (days)]	-14 to 1	1	14 [± 3]	28 [± 3]	56 [± 3]	84 [± 3]	112 [± 3]
Hepatitis panel [9] and HIV	X						
Backup sample		X				X	
Genomic samples		X					
PK sampling [10]		X	X[11]	X	X	X	
Urine drug screen	X						
		X				X	
Fasting prior to visit [12] and Record time of statin dose		X	X	X	X	X	
Study drug dispensing and accountability by IRT[13]		X	X	X	X	X	
Review adverse events		X	X	X	X	X	X
Review concomitant medications	X	X	X	X	X	X	X

1. A complete physical examination will be performed at screening. Targeted, symptom-directed physical examinations will be performed at all other study visits.
 2. Includes calcium, phosphorus, GGT, CPK, and albumin. See Appendix B for a complete list of analytes.
 3. Urine test for human chorionic gonadotropin at randomization.
 4. Only PT and aPTT at baseline.
 5. Includes TBG, TSH, total T3 and T4, and free T3 and T4 except for Screening (see footnote 6).
 6. Exclude TBG.
 7. Exclude ApoCIII.
 8. Free testosterone will be calculated from total testosterone, [REDACTED], and serum albumin.
 9. Includes hepatitis B, HBsAg, HCV, and HCVAb
 10. Patients will be instructed not to take study drug prior to PK sampling except for Week 2 (see footnote 11).
 11. Patients will fast and arrive at the study site in the morning and following a predose PK blood draw, be administered study drug. All other assessments will be performed except for ECG. At 4 hours post dose, a second blood draw for PK will be taken. Following the blood draw, patients may discontinue fasting. Patients will then rest for 30 minutes, after which an ECG will be performed.
 12. Patients should fast for at least 10 hours prior to the visit.
 13. Treatments include MGL-3196 100 mg, MGL-3196 60 mg, or placebo. Each patient will receive study drug bottles labeled as A and B. Patients will take 1 capsule from bottle A and 1 capsule from bottle B once daily in the morning. No study drug will be dispensed at Week 12 or Early Termination. Study drug accountability will not be assessed at baseline.

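### The TSH down-titration rule gives two different doses for the second reduction, lists no step from 60 mg, and does not say which rule governs when it meets the Week 4 PK reassignment

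*Protocol*

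**What the plan says.** The trigger is the same in the Protocol Synopsis, Protocol 3.1 and SAP 2.2: "TSH is below the lower limit of normal (LLN) with a >50% change from baseline confirmed on 2 consecutive assessments". The response follows: "the 100 mg dose would be decreased to 80 mg, and an 80 mg dose would be decreased to 60 mg". Two sentences later comes "A second down-titration is permitted (i.e. to 40 mg".

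The planned doses are set elsewhere. Every active patient starts on 100 mg. Between the Week 2 and Week 4 visits, "all patients randomized to drug will be treated with 60 mg of MGL-3196" (Protocol 1.2.2). At Week 4, patients whose Week 2 four-hour level was below 1,500 ng/mL go back to 100 mg. For those at or above it, "they will continue to receive 60 mg QD for weeks 4-12" (Protocol 5.1).

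Footnote 13 of Protocol Appendix A describes what is dispensed: "Treatments include MGL-3196 100 mg, MGL-3196 60 mg, or placebo". The final-dose analysis in SAP 3.7.3 also names only 100 mg and 60 mg.

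**The concern.** A dose rule for a safety trigger should give one answer for each dose a patient may be taking. This one gives two answers for the second reduction and none for a patient on 60 mg. At Week 4 it can also pull against the PK rule, which may raise the dose at the visit where the TSH rule calls for lowering it.

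Sites cannot settle this by judgement. Patients, sites and sponsor are blinded, and drug is assigned through the IRT (Protocol 5.3 and 5.5.2), so the dose map has to be written down beforehand. The unblinded clinical pharmacologist's stated dosing task is the PK-based assignment (Protocol 1.2.2). The patients kept on a dose with no listed step are those selected for the highest measured drug levels. Thyroid-axis change is a named safety objective.

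**Working it through.** **1. Apply the listed steps from each dose.** The inputs are 100 to 80 mg and 80 to 60 mg, and the figure to reproduce is 40 mg after a second reduction.

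| Dose before | After one listed step | After two listed steps | Stated after the second |
|---|---|---|---|
| 100 mg | 80 mg | 60 mg | 40 mg |
| 80 mg | 60 mg | none listed | 40 mg |
| 60 mg | none listed | none listed | 40 mg |

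The stated 40 mg is not reproduced from any starting dose. Three readings that might rescue it each fail:
- If 40 mg follows 60 mg, it is the third reduction from 100 mg, not the second.
- If the second reduction runs from 80 to 40 mg, it contradicts the listed 80 to 60 mg.
- If the planned Week 2 change from 100 to 60 mg counts as the first reduction, then 60 to 40 mg is the second. Protocol 10.2.1.1 does use the term down-titrated for that planned change. But the TSH rule does not count it, and its own first step is 100 to 80 mg.

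**2. Find when the rule can act on scheduled visits.** After the first dose, TSH is measured at Weeks 2, 4, 8, 12 and 16 (Protocol 9.8), and two consecutive assessments are needed.
- Weeks 2 and 4: confirmed at Week 4, when every active patient is on 60 mg and due for PK reassignment.
- Weeks 4 and 8: confirmed at Week 8, on 100 mg or 60 mg as assigned.
- Weeks 8 and 12: confirmed at Week 12, when treatment ends.

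So the missing 60 mg step is reached at Week 4 for anyone, and at Week 8 for the 60 mg group. At Week 4 a patient below the PK cut-off is due to go up to 100 mg and also to be reduced. The text does not say which rule governs, or whether the reduction starts from 60 mg or from the newly assigned dose.

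A second reduction is harder to reach. If it needs a fresh pair after a first reduction at Week 4, that pair is Weeks 8 and 12, too late to act on. It can be acted on at Week 8 only if the Week 4 result is counted twice, or sooner with unscheduled tests. The text does not say whether either is allowed.

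**3. Count the patients.** The plan is "70 patient to MGL-3196, 35 patients to placebo" (Protocol 10.2.4). On above-target exposure at 100 mg, Protocol 1.2.2 says variability "may occur in some (~25-30%) patients in the HeFH study who may have higher than the target exposure". That refers to exposure above 4000-9000 ng·hr/mL, not to the 1,500 ng/mL cut-off, so using it for the size of the 60 mg group is an assumption.
- 70 × 0.25 = 17.5 and 70 × 0.30 = 21, so about 18 to 21 on 60 mg in Weeks 4-12.
- 70 − 21 = 49 and 70 − 17.5 = 52.5, so about 49 to 52 on 100 mg.
- For a wider range, shares of 10% and 50% would give 7 and 35 on 60 mg.

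These are patients at risk of meeting the gap, before dropout. They are not expected triggers.

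**4. Check supply.** Each dose is one capsule from each of two bottles, in 40 mg, 60 mg or placebo. Then 40 + 0 = 40, 60 + 0 = 60, 40 + 40 = 80 and 60 + 40 = 100 mg.

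**The case against.** The strongest reply is that little depends on this. Protocol 1.2.3 regards such a TSH fall as very improbable, with target exposures at least 10-fold below those where suppression might be anticipated. The same section applies downward adjustment to any patient who shows the fall, which includes patients on 60 mg. The DSMB reviews thyroid effects and can advise on dosing, and Protocol 4.3 allows withdrawal for a severe laboratory abnormality. The SAP's primary comparison pools all active patients against placebo, so it needs no dose class, and the final-dose analysis is descriptive.

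All of that stands, and it limits the size of the problem. It does not supply the missing step, settle 60 mg against 40 mg, or rank the two Week 4 rules. A duty to lower the dose does not say to what.

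A reader might also infer more than the documents support:
- **That the rule cannot be carried out for most active patients.** On the protocol's estimate most are on 100 mg in Weeks 4-12, with a clear first step. More than 35 of 70 would have to be on 60 mg for this to hold.
- **That all 70 are exposed throughout Weeks 2-4.** On scheduled visits no trigger can be confirmed before Week 4, so a patient already reduced for TSH before that visit would need unscheduled tests.
- **That the 80 mg step is stray, or that 80 mg and 40 mg cannot be supplied.** 80 mg is where the first step from 100 mg leads, and the capsules make all four doses. Footnote 13 is worded as what treatments include, so it need not be exhaustive.

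**Conclusion.** The rule is inconsistent as written in all three places. The second reduction has two stated doses, 60 mg has no listed step, and precedence at Week 4 is unstated. The first two defects follow from the text alone. The count of about 18 to 21 of 70 rests on the proxy in step 3, and the timing rests on scheduled visits only.

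Few patients are likely to meet the problem. The missing 60 mg step and the Week 4 clash are the more reachable defects; the conflict over the second reduction needs an overlapping pair of results or unscheduled tests. It still warrants correction, because a safety rule has to work when it is triggered and blinded sites cannot improvise it. It does not follow that patients are left without protection against thyroid suppression.

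The analysis consequence is minor. A patient ending on 80 or 40 mg has no class in SAP 3.7.3. One who went from 100 to 80 to 60 mg would be grouped with patients kept on 60 mg for high drug levels.

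**What to change.** - Reconcile the Protocol Synopsis, Protocol 3.1 and SAP 2.2 into one rule with a stated response for every dose a patient can be on, and say whether the planned Week 2 change counts as a reduction. The sponsor and DSMB decide the steps; this review takes no view on the doses.
- State which rule governs when a TSH trigger coincides with the Week 4 PK reassignment, and from which dose any reduction starts.
- State whether a second reduction needs two new assessments or may reuse the previous one.
- Bring Appendix A footnote 13 into line with the doses the rule can produce.
- In SAP 3.7.3, state how patients on doses other than 100 or 60 mg, and patients who reach 60 mg through a TSH reduction, are classed.

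The cost is protocol and SAP wording and a check that the IRT carries the same dose map. No patients or visits are added.

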hsCRP	High-sensitivity C-reactive protein
ICF	Informed consent form

Abbreviation	Definition
ICH	International Conference on Harmonisation
IEC	Independent Ethics Committee
IRB	Institutional Review Board
IRT	Interactive Response Technology
ITT	Intent-to-Treat
IUD	Intrauterine device
LDL	Low-density lipoprotein
LDL-C	Low-density lipoprotein cholesterol
LH	Luteinizing hormone
LLN	Lower limit of normal
MedDRA	Medical Dictionary for Regulatory Activities
NASH	Non-alcoholic steatohepatitis
Non-HDL-C	Non-high-density lipoprotein cholesterol
OATP	Organic anion-transporting polypeptide
P1NP	Procollagen type 1 N-terminal propeptide
PCSK9	Proprotein convertase subtilisin/kexin type 9
PK	Pharmacokinetic
PT	Prothrombin time
QTcF	QT interval corrected using Fridericia's formula
RNA	Ribonucleic acid
SAE	Serious adverse event
SHBG	Sex hormone-binding globulin
T3	Triiodothyronine
T4	Thyroxine
TC	Total cholesterol
TEAE	Treatment-emergent adverse event
THR	Thyroid hormone receptor
THR- α	Thyroid hormone receptor alpha
THR- β	Thyroid hormone receptor beta
TSH	Thyroid stimulating hormone
ULN	Upper limit of normal
WHO	World Health Organization

1 INTRODUCTION AND BACKGROUND INFORMATION

1.1 Background

Madrigal Pharmaceuticals is developing MGL-3196 for the treatment of HeFH in adults receiving maximally tolerated statin therapy who require additional lowering of low density lipoprotein cholesterol (LDL-C). Despite advances in treatment, approximately 70% of high-risk cardiovascular (CV) patients do not achieve low-density lipoprotein cholesterol (LDL-C) goals, and as many as 10% of hypercholesterolemic patients do not tolerate statins.^{1,2} Elevated LDL-C levels are associated with CV disease, including myocardial infarctions and strokes, and drugs such as statins that lower LDL-C also reduce CV morbidity and mortality.

Heterozygous familial hypercholesterolemia (HeFH) and homozygous familial hypercholesterolemia (HoFH) are genetic disorders characterized by severe debilitating dyslipidemia and early onset CV disease. Individuals with HeFH typically have LDL-C levels approximately double that of unaffected siblings. HeFH is most commonly caused by mutations of the LDLR gene. If untreated, early onset coronary artery disease will likely develop in HeFH patients. The prevalence of HeFH is estimated to be 1 in 500 and may be as high as 1 in 200. Despite treatment with newer therapies (ie, proprotein convertase subtilisin/kexin type 9 [PCSK9] inhibitors) and standard care (which includes statins and ezetimibe), some HeFH patients are not achieving their LDL-C goal.³ A recent large registry study of HeFH patients revealed that patients receiving maximal therapy (i.e., statins with a potency of >45% LDL-C reduction plus at least another lipid-lowering agent) only 11.2% reach target LDL-C levels of <100 mg/dL.⁴

Thyroxine (T4) via its active derivative, T3, provides beneficial metabolic effects on cholesterol, triglycerides, and liver triglyceride levels, primarily through action at the THR- β , the predominant hepatocyte THR.^{5,6,7,8,9} However, excessive levels of thyroid hormone can lead to adverse effects, particularly in the heart and bones that are primarily mediated by the THR- α receptor which is the major systemic thyroid hormone receptor.^{10,11} MGL-3196 is a selective THR- β agonist with actions in the liver that is designed to avoid those systemic actions mediated through THR- α and the central thyroid action suppression observed with previous analogues.

There are several rationales for the use of MGL-3196 for the treatment of patients with genetic dyslipidemias, including HeFH and HoFH. Specifically, thyroid receptor β agonists have the potential to reduce LDL cholesterol by both LDL-receptor dependent and independent mechanisms, which include reduction in circulating PCSK9,¹² stimulation of hepatic cholesterol metabolism and excretion, potential reduction of ANGPTL3, and direct reduction of ApoB. The effect of thyroid β receptor agonism to reduce cholesterol in familial hypercholesterolemia (FH) has been demonstrated in mouse LDL-receptor knockout mice¹³ and in humans with HeFH treated with an earlier thyroid agonist, eprotirome.¹⁴ Thyroid beta agonists are one of the few mechanisms that has the potential to reduce lipoprotein(a), an atherogenic lipoprotein particle that is frequently elevated in patients with FH. MGL-3196 potently reduces triglycerides, providing additional cardiovascular benefit. In addition, MGL-3196's mechanism is complementary to statins and ezetimibe because thyroid β receptor agonists do not affect cholesterol synthesis pathways or intestinal absorption of cholesterol.

Thyroid hormone receptor analogs demonstrating an improved therapeutic window between beneficial lipid effects and adverse systemic effects have been developed and tested in clinical trials and demonstrated validation of cholesterol and triglyceride lowering.^{15,16} However, eprotirome and other analogs also demonstrated safety issues that resulted in discontinuation of clinical development. These include low margins relative to doses that suppress the central thyroid axis, elevated liver enzymes in Phase 1,2 and 3 studies, and other safety issues such as formation of a nitrated mutagenic impurity at gastric pH and collagen damage in a preclinical toxicology study.^{17,18} MGL-3196 has shown absence of these safety issues in preclinical and in clinical studies, so far, as described below.

